#### 2.2.3. Safety endpoints

1. Routine haematology, biochemistry, physical examination, vital signs, urinalysis, electrocardiogram (ECG).
2. Clinical adverse events (AEs) – particular note of use of sick day rules and Addisonian crises. Under or over-replacement with glucocorticoids will be considered in the efficacy endpoints.
3. Changes relative to the standard treatment in weight, body mass index (BMI), waist circumference, and blood pressure (BP).

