#### 2.4.2. Exploratory endpoints

1. Partial AUC of 17-OHP at 15:00-23:00, 23:00-07:00, and 07:00-15:00 (all refer to actual clock time of sampling).
2. The primary endpoint measure will also be presented for the profiles measured at 4 and 12 weeks for the purposes of titration.
3. Changes relative to standard treatment in the following:
  - a. Bone markers – serum CTX and osteocalcin (after fasting)
  - b. hsCRP
  - c. Assessment of glucose and insulin in the morning (after fasting)
  - d. Assessment of HbA1c, total testosterone, and PRA in the morning
  - e. QoL using SF-36®, MAF, and EQ-5D™
4. Use of glucocorticoids at beginning and end of the study will be presented both as individual glucocorticoids used, and as calculated hydrocortisone equivalents using accepted conversion constants for the calculations.

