### 8.2. Standard comparison methods

In general, continuous variables will be compared across treatment groups using a Normal analysis of covariance (ANCOVA) linear model including pre-baseline standard therapy and, if appropriate, the baseline assessment of the variable as covariates in the model. In the case of change-from-baseline variables, baseline will always be included as a covariate.

Binary variables, such as response, will be compared using logistic regression with adjustment for covariates as in the continuous data case.

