### 10.7.2. Bone markers and laboratory assessments of special interest

Changes relative to standard treatment in:

- a. Bone markers – serum CTX and osteocalcin (after fasting)
- b. hsCRP
- c. Assessment of glucose and insulin in the morning (after fasting)
- d. Assessment of HbA1c, total testosterone, and PRA in the morning

For the assessment of glucose and insulin, the homeostasis model assessment of insulin resistance (HOMA-IR) value (Wallace TM, 2004) will be calculated using fasting values with following formula:

$$\text{HOMA-IR} = [\text{glucose (mmol/L)} * \text{insulin (}\mu\text{U/mL)}] / 22.5.$$

Change from baseline will be calculated at each visit (Week 4, Week 12, and Week 24) and summary statistics will be presented for both absolute values and change from baseline for all bone markers and laboratory assessments of special interest listed above by treatment group, pre-baseline standard therapy and visit. Shift tables of baseline to minimum and maximum on-treatment will be produced for the appropriate parameters displaying the number and percentage of subjects in each of the categories (High, Low and Normal) relative to the category of their baseline assessment. Results considered clinically significant by the investigator will be summarised. Detailed listings will be produced for all bone markers and laboratory assessments of special interest. In addition, boxplots of change from baseline over time for each bone marker or laboratory assessment of special interest will be produced along with a line connecting the mean change through time.

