#### **SF-36®**

The SF-36® questionnaire is a multipurpose, generic, short-form health survey containing 36 questions (4-week recall) yielding 8 health domain scales and 2 psychometrically based physical and mental component summary measures (Maruish 2011). For each questionnaire, standardised scores will be generated using a validated scoring software package (QualityMetric Health Outcomes™ Scoring Software 4.5) to calculate scores for for the 8 health domain scales and 2 summary measures using algorithms specific to the questionnaire.

The two summary measures are referred to as the physical component score and mental component score.

The 8 health domain scales to be summarised are:

- Physical Functioning (PF)
- Role-Physical (RP)
- Bodily Pain (BP)
- General Health (GH)

- Vitality (VT)
- Social Functioning (SF)
- Role-Emotional (RE)
- Mental Health (MH)

For each summary measure and scale, the change from baseline and percentage change from baseline at week 24 will be calculated. Summary statistics for absolute values at each visit, change and percentage change from baseline at week 24 will be tabulated by treatment group and pre-baseline standard therapy.

Individual question scores, summary measure scores and scale scores will be listed.

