#### 11.5. Vital signs

The following vital signs will be collected: systolic blood pressure (SBP), diastolic blood pressure (DBP), pulse rate, respiratory rate, temperature, height, waist circumference, weight, BMI.

The change from baseline will be calculated and summary statistics will be tabulated for both absolute values and change from baseline by treatment group, pre-baseline standard therapy, and visit. Shift tables of baseline to minimum and maximum on-treatment will be created for the following vital signs: SBP and DBP. In addition, boxplots of change from baseline in vital signs over time will be produced along with a line connecting the mean change through time.

Vital signs will be listed and abnormal findings will be marked.

The following reference ranges will be used to determine the categories for the vital signs shift table, and to mark the abnormal (high/low) findings in the vital signs listing:

- Systolic blood pressure: Low < 100 mmHg; Normal  $\geq$  100 mmHg to  $\leq$  150 mmHg; High > 150 mmHg
- Diastolic blood pressure: Low < 60 mmHg; Normal  $\geq$  60 mmHg to  $\leq$  95 mmHg; High > 95 mmHg

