## **Efficacy**

Primary efficacy analysis for 17-OHP, change from baseline to 24 weeks in primary efficacy variable, analysis of covariance model (Efficacy evaluable analysis set)

*Repeat above 1 table for weeks 4 and 12*

Secondary efficacy analysis of 17-OHP by pre-treatment strata, change from baseline to 24 weeks in primary efficacy variable, analysis of covariance model (Efficacy evaluable analysis set)

*Repeat above 1 table weeks 4 and 12*

Summary of absolute values of primary efficacy variable for 17-OHP, by visit (Efficacy evaluable analysis set)

Summary of change in baseline in primary efficacy variable for 17-OHP, by visit (Efficacy evaluable analysis set)

Secondary efficacy analysis of responders at 09:00h week 24 for 17-OHP, logistic regression model (Efficacy evaluable analysis set)

Summary of the 17-OHP results at 09:00h week 24 (Efficacy evaluable analysis set)

*Repeat all 17-OHP only Efficacy outputs above for the A4 hormone (including repeats)*

*Repeat all Efficacy outputs above in the Full analysis set (including repeats)*

Secondary efficacy analysis of change from baseline to 24 weeks in body composition - Dual Energy X-ray Absorptiometry, analysis of covariance model (Efficacy evaluable analysis set)

Summary of absolute values of body composition - Dual Energy X-ray Absorptiometry (Efficacy evaluable analysis set)

Summary of change from baseline in body composition - Dual Energy X-ray Absorptiometry (Efficacy evaluable analysis set)

Exploratory analysis of 17-OHP 8-hour profiles: change from baseline to 24 weeks in primary efficacy variable, analysis of covariance model (Efficacy evaluable analysis set)

*Above partial profile ANCOVA table to be repeated for separate pre-baseline strata*

*All partial profile outputs above to be repeated for A4 hormone (total of 2 tables)*

Summary of change from baseline for bone markers and laboratory assessments of special interest (Efficacy evaluable analysis set)

Summary of absolute values for bone markers and laboratory assessments of special interest (Efficacy evaluable analysis set)

Shift table of baseline to minimum on-treatment for bone markers and laboratory assessments of special interest (Efficacy evaluable analysis set)

Shift table of baseline to maximum on-treatment for bone markers and laboratory assessments of special interest (Efficacy evaluable analysis set)

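### The exploratory marker and quality-of-life endpoints are defined against standard treatment, but SAP 10.7.2, 10.7.3 and table list 14.1 plan no between-arm estimate, contrary to the general ANCOVA rule in SAP 8.2

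*SAP*

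**What the plan says.** **Endpoint wording.** SAP 2.4.2 introduces the exploratory endpoints with "Changes relative to standard treatment in the following". It then lists CTX and osteocalcin, hsCRP, fasting glucose and insulin, HbA1c, total testosterone and PRA, and the three quality-of-life instruments. Protocol 7.3 has the same list, and protocol 13.6.3 repeats it among the exploratory efficacy analyses. SAP 10.7.2 opens its own list with "Changes relative to standard treatment in" and adds HOMA-IR as a derived value.

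**Planned analysis.** For the markers, SAP 10.7.2 says that "summary statistics will be presented for both absolute values and change from baseline for all bone markers and laboratory assessments of special interest". Shift tables, clinically significant results, listings and boxplots follow. For SF-36, SAP 10.7.3 says: "Summary statistics for absolute values at each visit, change and percentage change from baseline at week 24 will be tabulated by treatment group". MAF and EQ-5D follow the same pattern, with frequency and shift tables for the EQ-5D domains. No model, treatment difference or interval is named.

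**Table list.** SAP 14.1 carries entries such as "Summary of change from baseline for bone markers and laboratory assessments of special interest (Efficacy evaluable analysis set". ANCOVA tables appear there only for the hormone profiles and DEXA.

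**General rule.** SAP 8.2 says: "In general, continuous variables will be compared across treatment groups using a Normal analysis of covariance (ANCOVA) linear model". The covariates are pre-baseline therapy and, for change variables, always the baseline value. Protocol 13.1.3 says the same. SAP 7.1 makes Chronocort versus standard therapy the comparison throughout, and SAP 8.3 sets two-sided 95% intervals.

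**The concern.** The endpoint names a between-arm quantity and the general rule says how to estimate it, but the sections and tables that would deliver it stop at summaries by arm. A programmer working from 10.7.2, 10.7.3 and 14.1 would produce no treatment difference. One working from 8.2 would produce an ANCOVA with no table to hold it.

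At stake is how the exploratory results on cardiovascular risk, bone turnover, glucose metabolism and quality of life are read. Mean changes set side by side, without an interval, are easily over-read in either direction, and chance baseline imbalance between the arms goes uncorrected.

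**Working it through.** **1. The plan's own figure.** The documents give no precision or power for these endpoints. The only stated figure is for the primary endpoint (SAP 5): 102 evaluable subjects, falls of 0.78 and 0.2, SD 0.681, power above 95%. With 51 per arm (1:1 assumed, since the ratio is not stated), z = 0.58 / (0.681 × √(2/51)) − 1.96 = 4.30 − 1.96 = 2.34, so power is about 0.99. Also, 102 / 0.85 = 120. Both reproduce, and nothing here changes them.

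**2. Sections side by side.**

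| Variables | SAP section | Model named | ANCOVA table in 14.1 |
|---|---|---|---|
| 17-OHP, A4 24-hour profiles | 10.5, 10.6.1 | Yes, via 8.2 | Yes |
| DEXA | 10.6.2 | Yes, via 8.2 | Yes |
| 8-hour partial profiles (exploratory) | 10.7.1 | Yes, via 10.5 | Yes |
| Markers (exploratory) | 10.7.2 | No | No |
| Quality of life (exploratory) | 10.7.3 | No | No |

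Exploratory status does not explain the gap, because the partial profiles under the same 10.7 heading do get ANCOVA. SAP Section 12 records changes to shift tables and dose-level splits but nothing on this. Protocol 13 requires even minor changes of method to be documented in the SAP.

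**3. Number of variables.** Markers: CTX, osteocalcin, hsCRP, glucose, insulin, HOMA-IR, HbA1c, total testosterone, PRA = 9. SF-36: 8 scales + 2 summaries = 10. MAF: GFI = 1. EQ-5D: index by two methods + VAS = 3. Total 9 + 10 + 1 + 3 = 23. Leaving out HOMA-IR as a derived value and counting the EQ-5D index once gives 21.

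**4. What the planned tables allow.** SAP 8.1 gives N, mean and SD by arm, so a reader can form an unadjusted difference. In units of the SD of change, with 51 per arm, the 95% half-width is t × √(2/51) = 1.985 × 0.198 = 0.39. The difference detectable with 80% power is (1.960 + 0.842) × 0.198 = 0.55 SD. The adjusted difference also needs the baseline-to-change covariance, which is not tabulated. It could be backed out only if the baseline, week 24 and change SDs all came from the same subjects.

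**5. What adjustment would gain (illustrative).** Let r be the correlation between baseline and week 24, and assume equal variances at the two times. The variance of the ANCOVA difference relative to the raw change-score difference is (1 − r²) / (2(1 − r)) = (1 + r)/2.

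| r (assumed) | Variance ratio | 95% half-width, 0.393 × √ratio |
|---|---|---|
| 0.3 | 0.65 | 0.32 SD |
| 0.5 | 0.75 | 0.34 SD |
| 0.7 | 0.85 | 0.36 SD |

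The documents give no value of r for any of these variables.

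**The case against.** **The rule in 8.2 already covers these variables.** This is the strongest point. Nothing in 10.7.2 or 10.7.3 overrides 8.2, so a reader who infers that the SAP offers only within-arm summaries, or that the trial can yield no treatment difference, goes too far. The general rule stands and an unadjusted difference can be derived. What remains is that the rule is not carried into the sections or the table list. Whichever way the silence is read, some SAP text needs correcting.

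**The analyses are exploratory and declared limited.** SAP 10.7 says only a limited set is described, and SAP 2.4 allows ad hoc additions. This lowers the importance. It does not reconcile the endpoint wording with the tables.

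**Some objectives are met as planned.** The objectives for glucose, insulin, HbA1c and PRA (protocol 6.3, SAP 2.4.1) ask for changes from baseline, which the summaries by arm provide. One cannot say that the trial would fail to address its stated questions.

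**Safety variables.** A reader might extend the point to the safety endpoint "Changes relative to the standard treatment in weight, body mass index (BMI), waist circumference, and blood pressure (BP". The wording is comparative, but protocol 13.3.5 classes weight, BMI, waist and vital signs as safety variables, and protocol 13.7 plans only to list and summarise them. SAP 11.5 does so: "summary statistics will be tabulated for both absolute values and change from baseline by treatment group, pre-baseline standard therapy, and visit". The documents do not support calling this an omitted analysis.

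**More unadjusted intervals.** With 23 intervals and no true effect, 23 × 0.05 = 1.15 would exclude zero on average. If they were independent (an assumption), the chance of at least one would be 1 − 0.95²³ = 0.69. This is a real cost, which labelling makes visible but does not remove.

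**Conclusion.** The point holds as an internal inconsistency confined to the exploratory marker and quality-of-life endpoints, 21 to 23 variables depending on the count. They are defined relative to standard treatment and the general rule promises a baseline- and stratum-adjusted comparison, but the specific sections and the table list do not deliver it. SAP Section 12 does not declare the departure.

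The consequence is moderate. No primary or secondary conclusion is touched, and a cruder difference can be derived from the planned summaries. The 0.39 SD half-width rests on 51 per arm and 1:1 allocation. The gain from adjustment is illustrative only, since it rests on an assumed r and equal variances. The main evidence is the text comparison, not these figures.

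**What to change.** In SAP 10.7.2 and 10.7.3, state that week 24 change is analysed with the 8.2 ANCOVA, with the baseline value and pre-baseline therapy as covariates. Report the adjusted difference, Chronocort minus standard, with a 95% CI, labelled exploratory and not adjusted for multiplicity. Add the tables to 14.1. Clearly skewed markers may be analysed on the log scale and reported as a ratio of geometric means. That choice fits the masked review of distributions in protocol 13.10.

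If the sponsor prefers to stay descriptive, the minimum is to reword the endpoints accordingly and record the departure from 8.2 in Section 12. An adjusted difference for weight, BMI, waist and blood pressure is optional.

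The cost is a few sentences, reuse of a model already planned and some additional tables, plus the extra unadjusted intervals. Comparisons run without being in the SAP must be described as such in the study report (protocol 13.9).

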### 10.7.3. Quality of life (QoL) questionnaires

Changes relative to standard treatment in QoL at 24 weeks, measured using three instruments: SF-36®, MAF, EQ-5D™.

#### **SF-36®**

The SF-36® questionnaire is a multipurpose, generic, short-form health survey containing 36 questions (4-week recall) yielding 8 health domain scales and 2 psychometrically based physical and mental component summary measures (Maruish 2011). For each questionnaire, standardised scores will be generated using a validated scoring software package (QualityMetric Health Outcomes™ Scoring Software 4.5) to calculate scores for for the 8 health domain scales and 2 summary measures using algorithms specific to the questionnaire.

The two summary measures are referred to as the physical component score and mental component score.

The 8 health domain scales to be summarised are:

- Physical Functioning (PF)
- Role-Physical (RP)
- Bodily Pain (BP)
- General Health (GH)

- Vitality (VT)
- Social Functioning (SF)
- Role-Emotional (RE)
- Mental Health (MH)

For each summary measure and scale, the change from baseline and percentage change from baseline at week 24 will be calculated. Summary statistics for absolute values at each visit, change and percentage change from baseline at week 24 will be tabulated by treatment group and pre-baseline standard therapy.

Individual question scores, summary measure scores and scale scores will be listed.

### ***Multidimensional Assessment of Fatigue (MAF)***

The MAF is a self-administered questionnaire consisting of 16 questions. The Global Fatigue Index (GFI) will be calculated using a standard method specific to the MAF questionnaire. This combines the responses to the questionnaire to give one score ranging from 1 (no fatigue) to 50 (severe fatigue).

To calculate the GFI: Convert item #15 to a 0-10 scale by multiplying each score by 2.5 and then sum items #1, 2, 3, average #4-14, and newly scored item #15.

Scores range from 1 (no fatigue) to 50 (severe fatigue). Do not assign a score to items #4-14 if respondent indicated they "do not do any activity for reasons other than fatigue." If respondents select no fatigue on item #1, assign a zero to items #2-16. Item #16 is not included in the GFI.

The change from baseline and percentage change from baseline in GFI at week 24 will be calculated. Summary statistics for absolute values of GFI, change and percentage change from baseline at week 24 will be tabulated by treatment group and pre-baseline standard therapy.

Individual question scores and Global Fatigue index will be listed.

### ***EQ-5D™***

The EQ-5D™ questionnaire consists of two parts, the EQ-5D™ descriptive system and the EQ visual analogue scale (VAS). The descriptive system consists of 5 dimensions: mobility, self-care, usual activities, pain/discomfort and anxiety/depression. The EQ VAS is a visual scale in which the subject gives a single score between 0 and 100.

The results from the dimensions from will be combined using a standard method specially designed for the EQ-5D™ questionnaire to give a single index value (EuroQol Research Foundation). Two methods will be used to calculate the single index value:

**Method 1** will use the directly elicited 5L value set for the EQ-5D™ questionnaire as specified in Devlin 2016.

**Method 2** will use mapping approach described in van Hout 2012.

A table showing the frequency and percent of subjects with each score for each of the domains will be produced by treatment group and pre-baseline standard therapy. The change from baseline and percentage change from baseline will be calculated for both the single index value calculated from the 5 dimensions and the VAS score. Summary statistics for the absolute values of these two scores as well as change and percentage change from baseline at week 24 will be tabulated by treatment

group and pre-baseline standard therapy. Shift table of baseline to end of study will be produced by domain, pre-baseline therapy and treatment group.

Individual question scores for the EQ-5D™ descriptive system, the calculated single index value and EQ VAS score will be listed.

#### 10.7.4. Use of glucocorticoids

Use of glucocorticoids at visit 1 (baseline) and visit 4 (week 24) of the study will be presented as individual glucocorticoids used. Change in dose of last glucocorticoid from baseline to each visit will be presented as hydrocortisone equivalents using accepted conversion constants for the calculations (see Section 9.2.3).

A summary of the frequency and percent of subjects with total hydrocortisone dose equivalent increments versus baseline at each visit falling within the following categories:

- Dose increases versus baseline:
  - No increase observed ( $\leq 0$ mg),
  - $> 0$  to  $\leq 5$ mg increase,
  - $> 5$  to  $\leq 10$ mg increase,
  - $> 10$  to  $\leq 15$ mg increase,
  - $> 15$  to  $\leq 20$  mg increase,
  - $> 20$  to  $\leq 25$  mg increase,
  - $> 25$  to  $\leq 30$  mg increase and
  - $> 30$  mg increase.
- Dose decreases versus baseline:
  - No decrease observed ( $\leq 0$ mg),
  - $> 0$  to  $\leq 5$ mg decrease,
  - $> 5$  to  $\leq 10$ mg decrease
  - $> 10$  to  $\leq 15$ mg decrease,
  - $> 15$  to  $\leq 20$  mg decrease,
  - $> 20$  to  $\leq 25$  mg decrease,
  - $> 25$  to  $\leq 30$  mg decrease and
  - $> 30$  mg decrease.

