### **Rationale for the use of Chronocort® in the treatment of CAH**

Subjects with classic CAH receive replacement glucocorticoid and mineralocorticoid. Many different regimens of glucocorticoid are advocated. Hormone levels are monitored prior to morning dose of medication, aiming for mildly elevated morning 17-OHP levels and normal renin levels (Joint LWPES/ESPE CAH Working Group 2002; Merke 2005; Speiser 2003). Physical features and clinical symptoms are monitored for evidence of excessive (e.g. obesity, striae, and decreased linear growth in children) or insufficient (e.g. hirsutism, amenorrhoea or virilisation in women, fatigue, and increased linear growth, early puberty, advanced bone maturation in children) treatment. It is often quite difficult to reduce excess androgen without giving excess glucocorticoid because current therapies cannot replace the normal circadian rhythm of cortisol.

Chronocort® is a newly-developed formulation of hydrocortisone that allows for slow absorption after oral administration when given at 23:00 hours (20mg) and 07:00 hours (10mg), so that cortisol levels peak in the early morning (Whitaker 2014). The compound has the unique potential to provide the best possible physiologic replacement of cortisol and promises to ameliorate many of the unresolved medical issues surrounding the management of subjects with CAH (Mallappa 2015).

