#### 11.1.9 Visit 4 (Week 24) or early termination visit

##### Day 1

Subjects will attend the clinic on the morning of Day 1 and must be prepared for an overnight stay. The following assessments will be carried out and recorded;

- Subjects will be asked about any AEs and concomitant medication changes since the last visit
- An abbreviated physical examination, if indicated by AEs
- Record the time and dose of the last glucocorticoid medication taken prior to attending for this visit
- Vital signs

If the subject has been receiving their normal medication for the previous 5 days (i.e. sick day rules have not been applied in the preceding 5 days) they will be admitted to the clinic for their fourth 24-hour endocrine profile (17-OHP and A4). If sick day rules have been applied in the previous 5 days then the 24-hour profiling should be postponed until subjects have been receiving their normal medication for 5 days. The 24-hour endocrine profile sampling will commence at 15:00 hours on Day 1 followed by 2-hourly serum samples, hence 13 samples will be taken; 15:00, 17:00, 19:00, 21:00, 23:00, 01:00 (Day 2), 03:00, 05:00, 07:00, 09:00,

11:00, 13:00, 15:00 hours. These blood samples are to be taken within  $\pm 10$  minutes of the stated timepoints. If dosing needs to be conducted at the same timepoints as the blood sampling, the blood sampling should be conducted first before the dose of study medication is given.

## Day 2

On the second morning of Visit 4, the following will assessments will be conducted (the blood samples to be taken at 07:00 hrs before the morning dose of study medication):

- AEs
- Signs and symptoms of adrenal insufficiency
- Waist circumference will be measured, together with weight, and the BMI calculated
- The following questionnaires will be completed: MAF, SF-36® and EQ-5D™
- A full physical examination
- Vital signs
- ECG
- Urinalysis (including urine pregnancy test for females of childbearing age)
- Blood sample for fasting osteocalcin and CTX, insulin, glucose, HbA1c, lipids, hsCRP and total testosterone
- Blood samples will be taken for routine biochemistry and haematology
- PRA after the subject has been supine for 30 minutes
- DEXA scan at all sites except in Germany (this can be performed within 2 weeks of Visit 4)

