### 13.6.3 Exploratory Efficacy Analyses

1. Partial AUCs of 17-OHP at 15:00-23:00, 23:00-07:00, and 07:00-15:00 (all refer to actual clock time of sampling).
2. The primary endpoint measure will also be presented for the profiles measured at 4 weeks and 12 weeks for the purposes of titration.
3. Changes relative to standard treatment in the following:
  - a. Bone markers – serum CTX and osteocalcin
  - b. hsCRP
  - c. Assessment of glucose and insulin morning and evening (after fasting), HbA1c, total testosterone, and PRA
  - d. QoL using SF-36®, MAF, and EQ-5D™.
4. The comparison of the dose of individual glucocorticoids used, and as calculated hydrocortisone equivalents, and its change from baseline at 24-weeks.

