## 14. Appendix A – List of tables, listings and figures

### 14.1. List of planned tables

#### Study population

Subject disposition (All subjects)

Protocol deviations (All subjects)

Analysis sets (All subjects)

Demographic characteristics (Safety analysis set)

Baseline disease characteristics (Safety analysis set)

CAH medical history (Safety analysis set)

Other medical history excluding CAH events (Safety analysis set)

Prior medications (Safety analysis set)

Concomitant medications excluding steroids (Safety analysis set)

Use of sick day medication and steroids taken in addition to IMP (Safety analysis set)

Subject compliance (Safety analysis set)

Use of glucocorticoids: last dose prior to each visit (Safety analysis set)

Table of change from baseline to each visit in dose (hydrocortisone equivalent) of last glucocorticoid (Safety analysis set)

Categories of hydrocortisone dose equivalent increments versus baseline (Safety analysis set)

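### The continuous glucocorticoid change tables use the single last dose before a morning visit, so in the Chronocort arm they mix a shift in dosing over the day with a change in daily dose

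*SAP*

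**What the plan says.** Protocol 13.6.3 lists as an exploratory analysis: "The comparison of the dose of individual glucocorticoids used, and as calculated hydrocortisone equivalents, and its change from baseline at 24-weeks". It does not say whether the dose is daily or a single intake.

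SAP 10.7.4 settles on the last dose for the continuous presentation: "Change in dose of last glucocorticoid from baseline to each visit will be presented as hydrocortisone equivalents". Two planned tables in SAP 14.1 repeat this in their titles: "Use of glucocorticoids: last dose prior to each visit (Safety analysis set" and "Table of change from baseline to each visit in dose (hydrocortisone equivalent) of last glucocorticoid (Safety analysis set".

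The visit schedule collects a matching item. At Visit 4 (Protocol 11.1.9), as at Visits 1 to 3, the instruction is: "Record the time and dose of the last glucocorticoid medication taken prior to attending for this visit". The same section fixes the time of attendance: "Subjects will attend the clinic on the morning of Day 1 and must be prepared for an overnight stay".

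SAP 10.7.4 also plans a banded summary of "total hydrocortisone dose equivalent increments versus baseline at each visit". It does not say that the total is per day, and the matching title in SAP 14.1 omits the word.

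**The concern.** In the Chronocort arm the dosing pattern changes at randomisation. Protocol Sections 8 and 10.3 put about one third of the daily dose at 07:00 and two thirds at 23:00. In the standard arm the timing and the drugs must stay as they were (Protocol Section 8, Dose Adjustment). A comparison of one intake at baseline with one intake later therefore carries a pattern shift in one arm only.

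The protocol's rationale (Section 8) is that Chronocort improved androgen control in phase II without raising glucocorticoid exposure. A reader who asks whether that held here would turn to these tables. They could show a dose fall or rise that did not occur, or miss one that did.

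**Working it through.** **Inputs**
- Chronocort at 30 mg/day: 20 mg at night and 10 mg in the morning (Protocol Section 8, baseline assessment).
- Daily dose carried over at the switch as the hydrocortisone equivalent of baseline therapy, up to a 30 mg starting cap (Protocol Section 8).
- Conversion factors: prednisone or prednisolone 5, dexamethasone 80 (SAP 9.2.3).
- Share s of the standard daily dose taken as the last intake before attendance: not in the documents. Standard therapy follows site practice (Protocol 10.3). I assume a range of 25% to 100%.

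**The plan's own conversion.** SAP 9.2.3 converts 6 mg/day of prednisone: 6 × 5 = 30 mg/day. This reproduces, and it is a daily figure.

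**Redistribution with the daily dose unchanged at 30 mg.** Apparent change = Chronocort morning dose - baseline last dose = 10 - 30s.

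| Baseline share s | Baseline last dose (mg) | Chronocort 07:00 dose (mg) | Apparent change (mg) | True daily change (mg) |
|---|---|---|---|---|
| 25% | 7.5 | 10 | +2.5 | 0 |
| 1/3 | 10 | 10 | 0 | 0 |
| 1/2 | 15 | 10 | -5 | 0 |
| 2/3 | 20 | 10 | -10 | 0 |
| 100% | 30 | 10 | -20 | 0 |

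A standard-arm subject with no titration, and with the same dose of the day recorded each time, shows 0.

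**If the 07:00 Chronocort dose has not been taken before attendance.** The last intake is then the 23:00 dose, and the apparent change is 20 - 30s. With s = 1/2 this is 20 - 15 = +5 mg, again with no change in daily dose.

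**Evening-only titration.** The blinded physician may advise a change to the evening dose alone (Protocol Section 8; SAP 11.1). As arithmetic only: if the 23:00 dose moved by 5 mg, the daily dose would move by 5 mg and the recorded 07:00 dose by 0. This needs no assumption about s. It can also happen in the standard arm, but on Chronocort the unmeasured part is about two thirds of the day's dose.

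**Scale.** Phase II mean daily doses were 28 mg on standard therapy and 26 mg on Chronocort (Protocol Section 5), a difference of 26 - 28 = -2 mg. At a share of one half or more, redistribution alone exceeds that.

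**The case against.** **The section does not rest on the last dose alone.** The banded summary refers to a total, and its bands run beyond 30 mg in each direction. That suits a daily dose better than a 10 mg morning dose. This stands. A reader might infer that the endpoint as a whole replaces daily dose with last dose; the documents do not support that. The bands do not repair the continuous tables, however. If the total does mean daily, the two outputs can disagree for the same subject: -20 mg in one and no change in the other.

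**Last glucocorticoid could mean the last regimen before the visit.** SAP 9.2.3 converts daily doses and adds the components of combinations, and SAP 9.1 has a convention for middle doses, so regimens are held by time of day. But the table title refers to the last dose before each visit, the visit item asks for the time and dose of one intake, and SAP 10.4 says total daily dose when it means that. The single-intake reading fits the text better.

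**Direction and size rest on an undocumented share.** This also stands. A reader might infer that the tables will show a spurious steroid-sparing effect. They may instead show nothing or a rise, and the -20 mg case needs once-daily morning dosing, whose frequency the documents do not give.

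**The endpoint is exploratory.** SAP 10.7.4 plans description without a model or test, and titrations, unplanned changes and dosing instructions are reported elsewhere (SAP 11.1, 14.1). A misleading table could be checked against these. That limits the harm but does not make the table measure glucocorticoid use.

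**Conclusion.** The concern holds for the continuous tables. Followed as written, they compare one baseline intake on the standard regimen with one Chronocort intake that is normally about a third of the day's dose. The difference is not a measure of change in glucocorticoid use.

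For an unchanged 30 mg/day the artefact runs from +2.5 to -20 mg over the assumed shares, is 0 at one third, and can be a rise if the 23:00 dose is the one recorded. Its direction in the trial cannot be predicted from the documents. The illustration assumes an equal daily dose before and after the switch; above the 30 mg cap, part of a fall would be real.

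The categorical summary may already be on a daily basis, but the SAP does not say so. The primary analysis is untouched. What is at stake is any statement comparing steroid dose between arms.

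**What to change.** In SAP 10.7.4 and the matching titles in 14.1, define both the continuous and the categorical presentations as the total daily hydrocortisone-equivalent dose of the regimen in force at each visit, summed over all doses of the day.

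Name the source for each side of the change:
- **Baseline:** the CAH medication recorded separately from other medication (Protocol 10.6 and 11.1.1), which should also supply the starting-dose conversion. SAP 11.1 alone is not enough, because it covers study drug and the Chronocort arm's baseline regimen precedes it.
- **On treatment:** the dosing instructions and exposure data that SAP 11.1 already lists.

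Present the change at week 24 by arm, and keep the last-dose record as a listing only.

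The cost is SAP wording and the derivation behind these tables. No new assessment or data item is needed.
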